8.3.2. Method of Detecting AEs and SAEs

- The method of recording, evaluating, and assessing causality of AEs and SAEs and the procedures for completing and transmitting SAE reports are provided in [Appendix 3](#).
- Care will be taken not to introduce bias when detecting AE and/or SAE. Open-ended and non-leading verbal questioning of the participant is the preferred method to inquire about AE occurrence.

8.3.3. Follow-up of AEs and SAEs

- After the initial AE/SAE report, the investigator is required to proactively follow each participant at subsequent visits/contacts. All SAEs, and non-serious AEs of special interest (as defined in Section [2.3.1](#)), will be followed until the event is resolved, stabilized, otherwise explained, or the participant is lost to follow-up (as defined in Section [7.3](#)). Further information on follow-up procedures is given in [Appendix 3](#).

8.3.4. Regulatory Reporting Requirements for SAEs

- Prompt notification by the investigator to the sponsor of a SAE is essential so that legal obligations and ethical responsibilities towards the safety of participants and the safety of a study intervention under clinical investigation are met.
- The sponsor has a legal responsibility to notify both the local regulatory authority and other regulatory agencies about the safety of a study intervention under clinical investigation. The sponsor will comply with country-specific regulatory requirements relating to safety reporting to the regulatory authority, Institutional Review Boards (IRB)/Independent Ethics Committees (IEC), and investigators.
- Investigator safety reports must be prepared for suspected unexpected serious adverse reactions (SUSAR) according to local regulatory requirements and sponsor policy and forwarded to investigators as necessary.
- An investigator who receives an investigator safety report describing a SAE or other specific safety information e.g., summary or listing of SAE) from the sponsor will review and then file it along with the Investigator's Brochure and will notify the IRB/IEC, if appropriate according to local requirements.

8.3.5. Pregnancy

Not applicable for this study.

8.3.6. Cardiovascular and Death Events

Not applicable for a healthy volunteer study

8.3.7. Disease-Related Events and/or Disease-Related Outcomes Not Qualifying as SAEs

Not applicable for this study.

8.3.8. Medical Device Incidents (Including Malfunctions)

Not applicable for this study.

8.4. Treatment of Overdose

For this study, any dose of greater than 1 FDC tablet of DTG 50 mg / RPV 25 mg within a 24-hour time period will be considered an overdose.

Sponsor does not recommend specific treatment for an overdose.

In the event of an overdose, the investigator/treating physician should:

1. Contact the Medical Monitor immediately.
2. Closely monitor the participant for AE/SAE and laboratory abnormalities until study intervention can no longer be detected systemically (at least 25 days).
3. Obtain a plasma sample for PK analysis within 1 day from the date of the last dose of study intervention if requested by the Medical Monitor (determined on a case-by-case basis).
4. Document the quantity of the excess dose as well as the duration of the overdosing in the CRF.

Decisions regarding dose interruptions or modifications will be made by the investigator in consultation with the Medical Monitor based on the clinical evaluation of the participant.

8.5. Pharmacokinetics

8.5.1. Blood Sample Collection

- Blood samples for pharmacokinetic analysis of DTG and RPV will be collected at the time points indicated in SoA. The 4-hour post-dose sample must be drawn prior to the subjects' first post-dose meal. The actual date and time of each blood sample collection will be recorded.
- For each DTG PK sample, 2 mL of blood will be collected into di-potassium ethylenediaminetetraacetic acid (K₂EDTA) tubes for DTG quantification and **protected from light**.

- For each RPV PK sample, 2 mL of blood will be collected into sodium heparin tubes for RPV quantification and **protected from light**.
- Processing, storage and shipping procedures are provided in the Study Reference Manual provided by the site or other equivalent document. **Please pay special attention to the light protection procedures for both DTG and RPV collections and processing.**

8.5.1.1. Sample Processing Procedures

- If a cannula is used, the cannula will be inserted into an arm vein within sufficient time prior to dosing, will be kept patent with normal saline, and will be removed after the last blood sample is collected or earlier if the subject requests. To avoid artificial dilution of the PK samples by saline, 1 mL of whole blood will be collected and discarded before each whole blood sample is collected.
- Collect each serial whole blood PK sample as close as possible to the planned time relative to dosing detailed in the protocol. Collect a whole blood (2 mL) sample into a properly labelled K₂EDTA evacuated blood collection tube for DTG and a properly labelled sodium heparin tube for RPV. Record the date and exact time that each sample is collected in the CRF. All samples should be **protected from light** at all times by putting them in closed boxes, wrapping with aluminium foil or handling under yellow light.

8.5.1.2 Sample Storage Conditions

For DTG PK samples, immediately after collection, gently invert (**do not shake**) the blood collection tube 8-10 times to mix the K₂EDTA anti-coagulants with the whole blood and place the samples at room temperature **protected from light**. For RPV PK samples, immediately after collection, gently invert (**do not shake**) the blood collection tube 8-10 times to mix the sodium heparin anti-coagulants with the whole blood and place the samples at room temperature **protected from light**.

- All samples **must be protected from light** at all times by putting them in closed boxes, wrapping with aluminium foil or handling under yellow light.
- Within 45 minutes of sample collection for both DTG and RPV, centrifuge for 10 minutes, at 1500 - 2000 G, in 4°C.
- Within 30 minutes of centrifugation, using a polyethylene pipette, transfer plasma into separate, single, and appropriately labelled 2 mL Amber/Brown Sarstedt tubes.
- Immediately freeze the storage tubes in an upright position at -20°C.

DTG and RPV are photosensitive so all plasma sample manipulation procedures (sample collection and analytical steps) will be performed protecting samples from light. Limit the time between centrifugation and transfer of the plasma to amber/brown tubes as much as possible, with care to close the centrifuge lid between the different actions. If it is not possible to transfer the blood to plasma immediately; the centrifuged tubes should remain protected from light at all times (boxes or foil).

8.5.2. Sample Analysis

Dolutegravir will be extracted from plasma using protein precipitation followed by ultra performance liquid chromatography triple quadrupole mass spectrometry (UPLC-MS/MS) using the previously validated method, Quantitation of GSK1349572 in Human Plasma via UPLC with MS/MS Detection (PPD method number, P1170.02; [GlaxoSmithKline Document Number [2015N231443_00](#)]. The analysis will be performed by PPD, [name]. The DTG sample analysis will be under the management of Bioanalysis, Immunogenicity and Biomarkers (BIB), PTS, GlaxoSmithKline. Raw data will be archived at the bioanalytical site.

Rilpivirine will be extracted from plasma using protein precipitation followed by UPLC-MS/MS using the previously validated method, validation of a method for the determination of JNJ-16150108 (PRA-NL-SML-2159/JJP110EL-181103-C/BA13223). The potential conversion of rilpivirine to the Z-isomer will be evaluated as part of the rilpivirine sample analysis. The analyses will be performed by PRAHS, [name]. The RPV sample analysis will be under the management of Janssen. Raw data will be archived at the bioanalytical site.

Dolutegravir and rilpivirine sample analyses will be performed under light protection procedures.

8.6. Pharmacodynamics

Pharmacodynamic parameters are not evaluated in this study.

8.7. Genetics

Genetics are not evaluated in this study.

8.8. Biomarkers

Biomarkers are not evaluated in this study.

9. STATISTICAL CONSIDERATIONS

9.1. Statistical Hypotheses

This study will seek to characterize the pharmacokinetics of DTG and RPV following a single oral dose of DTG/RPV 50 mg/25 mg FDC in healthy, adult Japanese subjects. Also, this study will seek to assess the safety and tolerability of DTG/RPV 50 mg/25 mg FDC in healthy, adult Japanese participants. No formal statistical hypothesis will be tested.

9.2. Sample Size Determination

Approximately 16 participants will be enrolled and assigned to study intervention such that 13 evaluable participants complete the study.

There was no formal calculation of power or sample size for this study.

9.2.1. Sample Size Assumptions

Based on the previous DTG and RPV BE study (Study 201676) [GlaxoSmithKline Document Number [2015N243078_01](#)], the intersubject coefficients of variation (CVs) for AUC0-t, AUC0-inf and Cmax of a single dose of DTG+RPV (given as either single components or a fixed dose combination formulation) in a fed state were estimated to be less than or equal to 43.66% in healthy non-Japanese adult subjects. Using a conservative estimate of 43.66% for intersubject CV and a sample size of 13 subjects, the true mean AUC0-t, AUC0-inf and Cmax of DTG+RPV FDC were estimated to be within 80% to 125% of the observed geometric means with 95% confidence.

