Secondary To evaluate the safety and tolerability of DTG/RPV FDC in healthy, adult Japanese participants.	Safety and tolerability parameters, adverse event (AE)/serious adverse events (SAE), observed and change from baseline clinical laboratory values, and vital sign assessments.

$AUC_{(0-t)}$ = area under the plasma concentration time curve from time zero to the last quantifiable time point

$AUC_{(0-\infty)}$ = area under the plasma concentration time curve from time zero to infinity

$AUC_{(0-24)}$ = area under the plasma concentration time curve from time zero to 24 hours

$AUC_{(0-72)}$ = area under the plasma concentration time curve from time zero to 72 hours

$\%AUC_{ex}$ = % of $AUC_{(0-\infty)}$ that was extrapolated

C_{max} = maximum observed concentration

C_{24} = concentration at 24h post-dose

C_t = last quantifiable concentration

t = time of last quantifiable concentration

t_{lag} = absorption lag time

t_{max} = time of maximum observed concentration

λz = apparent elimination rate constant

$t_{1/2}$ = the elimination half-life

CL/F = apparent oral clearance

Vz/F = apparent oral volume of distribution

Overall Design:

This will be a single-center, single dose, open-label study in adult Japanese healthy participants to evaluate the PK, safety and tolerability of the DTG/RPV 50 mg/25mg FDC tablet. The study will consist of screening, treatment and follow-up phases. Participants will have a screening visit within 28 days prior to receiving the study intervention. Enrolled participants will receive a single oral dose of the DTG/RPV 50 mg/25 mg FDC tablet in a fed state. Safety assessments including, clinical laboratory safety tests and adverse event reports will be performed throughout the study. Serial PK samples will be collected pre-dose through 264 hours post-dose. All participants will have a follow-up visit within 12-17 days after the last dose of study intervention.

Disclosure Statement: This is a single group, single arm study that has no masking.

Number of Participants:

A maximum of 16 healthy adult Japanese subjects will be enrolled such that a minimum of approximately 13 evaluable subjects complete the study with at least 3 participants of each gender enrolled.

Intervention Groups and Duration:

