7.2. Participant Discontinuation/Withdrawal from the Study

- A participant may withdraw from the study at any time at his/her own request, or may be withdrawn at any time at the discretion of the investigator for safety, behavioral, compliance or administrative reasons. This is expected to be uncommon.
- If withdrawal is after Day 3, but before Follow Up procedure, please perform all Follow Up procedures as per SoA.
- The participant will be permanently discontinued both from the study intervention and from the study at that time.
- If the participant withdraws consent for disclosure of future information, the sponsor may retain and continue to use any data collected before such a withdrawal of consent.
- If a participant withdraws from the study, he/she may request destruction of any samples taken and not tested, and the investigator must document this in the site study records.

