9.4. Statistical Analyses

Final analyses will be performed after the completion of the study and final dataset authorization.

Data will be listed and summarized according to GlaxoSmithKline reporting standards where applicable.

Unless stated otherwise, descriptive summaries for continuous variables will include n, mean, standard deviation (SD), median, minimum, maximum; whereas, n and percent will be used as summary statistics for categorical variable. Geometric mean with

associated 95% CI, and the between-subject coefficient of variance (CV) (%CVb) for the geometric mean will be included for PK variables, where applicable.

Baseline or pre-dose assessment is the last available assessment prior to time of the first dose unless it is specified otherwise. If there are multiple assessments collected on the same scheduled time, the average of these assessments will be used. For tabulated safety summaries, only the scheduled assessments will be included in the summary tables.

Version 9.4 or higher of the Statistical Analysis Software (SAS) system will be used to analyze data as well as to generate tables, listings, and figures.

Complete details will be documented in the Reporting and Analysis Plan (RAP).

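### Does the 80% to 125% precision band for 13 subjects in Protocol 9.2.1 fail because it takes the variance as known?

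*Protocol*

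**What the plan says.** Protocol 9.2.1 takes its variability from an earlier bioequivalence study of the two drugs. The intersubject CVs for AUC(0-t), AUC(0-inf) and Cmax, for single components or the fixed-dose combination in the fed state, "were estimated to be less than or equal to 43.66% in healthy non-Japanese adult subjects". It then argues: "Using a conservative estimate of 43.66% for intersubject CV and a sample size of 13 subjects", the true means "were estimated to be within 80% to 125% of the observed geometric means with 95% confidence". It names no formula, distribution or quantile.

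The surrounding text claims little for this figure. Protocol 9.2 states: "There was no formal calculation of power or sample size for this study". Protocol 9.1 states: "No formal statistical hypothesis will be tested". The synopsis caps enrolment at 16, "such that a minimum of approximately 13 evaluable subjects complete the study".

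For the analysis, Protocol 9.4 plans a geometric mean with "associated 95% CI, and the between-subject coefficient of variance (CV) (%CVb) for the geometric mean will be included for PK variables". SAP 8.1.4 plans the same interval beside the SD of the log-transformed data. Neither document says whether the interval uses a t or a normal quantile. SAP 8.1.4 and 10.4.3 defer to company display standards that are not available here.

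**The concern.** The stated band can be reproduced only with a normal quantile, that is, with the variance treated as known. The study will estimate its variance from about 13 subjects, and the usual interval for a geometric mean then uses a t quantile with 12 degrees of freedom. At an observed CV of 43.66% that interval is wider than 80% to 125%, and the band is first met with 16 evaluable subjects.

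The sentence is also the only quantitative support for 13 in either document. Protocol 9.2.2 offers no sensitivity analysis, and SAP 10.6.1 says that withdrawn subjects were not replaced. If the band were wrong, the sole rationale for the size of a study with PK as its primary objective would overstate its precision. A reader could then be surprised by a wider reported interval although nothing had gone wrong.

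**Working it through.** **Inputs.** CV = 43.66%, n = 13, confidence 95% and band 80% to 125%, all from Protocol 9.2.1. Assumptions: log-normal PK parameters and a two-sided interval.

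**1. Reproduce the Protocol's figure.**
- Log-scale SD: σ = √ln(1 + 0.4366²) = 0.4177.
- Standard error: 0.4177/√13 = 0.1158.
- Limits with the CV taken as known: exp(±1.960 × 0.1158) = exp(±0.2271), or 79.7% to 125.5%. At whole-percent rounding, taking 125.49% to 125%, this is the stated band.
- Confidence carried by the fixed band: ln(1.25) = 0.2231, and 2Φ(0.2231/0.1158) − 1 = 2Φ(1.926) − 1 = 94.6%, or 95% to the whole percent.
- Strict sample size: (1.960 × 0.4177/0.2231)² = 13.46, so 14. At n = 14 the limits are 80.35% to 124.46%.
- The shortfall at n = 13 disappears if the CV is 42.84% instead of 43.66%.

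Other constructions do not give 80% to 125%. With the CV used directly as the log SD, the normal limits are 78.9% to 126.8%. A 90% t interval gives 81.3% to 122.9%.

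**2. The t interval.** Formula: exp(±t × 0.4177/√n), with an observed CV of 43.66%.

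| n | t quantile | Limits |
|---|---|---|
| 13 | 2.179 | 77.7% to 128.7% |
| 14 | 2.160 | 78.6% to 127.3% |
| 15 | 2.145 | 79.3% to 126.0% |
| 16 | 2.131 | 80.05% to 124.93% |

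At n = 13 the t interval stays within the band if the observed CV is about 38.2% or less.

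**3. Which calculation matches the sentence?** Protocol 9.2.1 fixes the band in advance and plugs in a CV. The chance that the true mean lies within a fixed ratio of the observed geometric mean depends on the true σ and n only. It does not depend on how the SD is later estimated, so the normal calculation in step 1 is the correct one. The t interval in step 2 has a random width set by the study's own SD. The Protocol does not say that the reported interval will have limits of 80% and 125%.

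**4. How conservative are the inputs?** The documents give no CV for each parameter, so a range is shown. Confidence carried by the fixed band:

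| CV | n | Confidence |
|---|---|---|
| 43.66% | 13 | 94.6% |
| 43.66% | 14 | 95.4% |
| 43.66% | 16 | 96.7% |
| 40% | 13 | 96.3% |
| 35% | 13 | 98.2% |
| 30% | 13 | 99.4% |

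**5. Quantile against sampling variation.** At n = 13 and an observed CV of 43.66%, moving from the normal to the t quantile shifts the upper limit from 125.5% to 128.7%, or 3.2 points. If the true CV is 43.66%, sampling variation in the SD alone spreads the upper t limit from about 117% to 142% (central 95% of the SD distribution). No planning sentence could fix the reported width closely.

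**The case for a change.** The strongest case for a change is that, in a study with no test, expected precision is the whole sample-size rationale, and it should describe the interval that will be reported. That interval will sit beside an SD estimated from the same subjects. If the true CV is 43.66%, a t-based 95% interval falls wholly inside 80% to 125% with probability 33% at n = 13 and 55% at n = 16. A normal interval with an estimated SD would cover only 92.6% at n = 13. The correction would cost one sentence.

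The arithmetic stands, and so do three points: the approximation is unlabelled, 14 subjects are strictly needed, and a reader who takes the band as a forecast of the reported limits would be misled at a CV of 43.66%. The inference does not stand. The 33% and 55% are assurance figures, and the Protocol claims no assurance. The 92.6% belongs to a normal interval with an estimated SD, which neither document proposes. The rewrite to 78% to 129% rests on a t quantile that neither document names. The Protocol's own description of 43.66% as an estimate it is using already signals a plug-in value.

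**Conclusion.** The sentence in Protocol 9.2.1 is right at the precision it states. With the CV taken as 43.66% and n = 13, the limits are 79.7% to 125.5% and the fixed band carries 94.6% confidence. The strict gap is 0.3 points on the lower limit, 0.5 on the upper and 0.4 points of confidence, or one subject. The wider figure of 78% to 129% describes a post-study t interval at that same observed CV; it does not contradict the sentence.

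Nothing depends on the gap. The study tests no hypothesis and claims no formal sample size calculation, and no decision is tied to 80% to 125%. The CV is an upper bound over parameters and formulations, and 13 is the planned minimum out of up to 16. Protocol 7.2 says of withdrawal: "This is expected to be uncommon". An analyst will compute the reported interval from the observed SD whatever the planning sentence says. Saying that the figure treats the CV as known, uses a normal quantile and is rounded would be a courtesy to the reader, with no gain for the trial.

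This rests on log-normal data and a two-sided 95% level, which the documents do not spell out.

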9.2.2. Sample Size Sensitivity

Not applicable.

9.3. Populations for Analyses

All of the data that is databased will be presented in subject listings and where appropriate presented in summary tables.

For purposes of analysis, the following populations are defined:

Population	Description
Screened	All participants who sign the ICF
Safety	All participants who enrolled in the study and received at least one dose of study drug.
Pharmacokinetic (PK)	All participants in the Safety population for whom a PK sample was obtained and had evaluable PK assay results.

9.4. Statistical Analyses

Final analyses will be performed after the completion of the study and final dataset authorization.

Data will be listed and summarized according to GlaxoSmithKline reporting standards where applicable.

Unless stated otherwise, descriptive summaries for continuous variables will include n, mean, standard deviation (SD), median, minimum, maximum; whereas, n and percent will be used as summary statistics for categorical variable. Geometric mean with

associated 95% CI, and the between-subject coefficient of variance (CV) (%CVb) for the geometric mean will be included for PK variables, where applicable.

Baseline or pre-dose assessment is the last available assessment prior to time of the first dose unless it is specified otherwise. If there are multiple assessments collected on the same scheduled time, the average of these assessments will be used. For tabulated safety summaries, only the scheduled assessments will be included in the summary tables.

Version 9.4 or higher of the Statistical Analysis Software (SAS) system will be used to analyze data as well as to generate tables, listings, and figures.

Complete details will be documented in the Reporting and Analysis Plan (RAP).

9.4.1. Efficacy Analyses

Not Applicable.

9.4.2. Safety Analyses

Safety data will be presented in tabular format and summarized descriptively according to GSK's Integrated Data Standards Library (IDSL) standards. No formal statistical analysis of the safety data will be conducted. All safety data will be listed.

Full details will be provided in the Reporting and Analysis Plan.

All safety analyses will be performed on the Safety Population.

9.4.3. Pharmacokinetic Analysis

Pharmacokinetic analysis will be the responsibility of the Clinical Pharmacology Modelling & Simulation department within GlaxoSmithKline, or its designee.

Plasma DTG and RPV concentration-time data will be analyzed by non-compartmental methods with Phoenix WinNonlin version 6.3 or higher. Calculations will be based on the actual sampling times recorded during the study.

From the plasma concentration-time data, please refer Objectives and Endpoints (Section 3), for the pharmacokinetic parameters that will be determined, as data permit.

Pharmacokinetic data will be listed and may be presented in graphical form and will be summarized descriptively. All pharmacokinetic data will be stored in the Archives, GlaxoSmithKline Pharmaceuticals, R&D. Statistical analyses of the pharmacokinetic parameter data will be the responsibility of Clinical Statistics, GlaxoSmithKline.

Full PK analyses will be described in the reporting and analysis plan.

